3.15 Study flow

[figure not shown]

Figure 4. The flowchart of this randomized crossover trial showing 4 random intervention sequences out of 24 permutations generated. Intervention A: MN + 1 FTU EMLA 30 minutes application; Intervention B: MN + 0.5 FTU EMLA 30 minutes application; Intervention C: MN + 1 FTU EMLA 15 minutes application; Intervention D: 1 FTU EMLA Only 30 minutes (controls)

| | | | |
|------|------|------|------|
| ABCD | BACD | CADB | DABC |
| ACBD | BADC | CABD | DACB |
| ABDC | BDAC | CBAD | DBAC |
| ACDB | BDCA | CBDA | DBCA |
| ADBC | BCAD | CDAB | DCAB |
| ADCB | BCDA | CDBA | DCBA |

Table 1. The exhaustive list of permutations of intervention sequences that will be randomized to the participants of this trial. Intervention A: MN + 1 FTU EMLA 30 minutes application; Intervention B: MN + 0.5 FTU EMLA 30 minutes application; Intervention C: MN + 1 FTU EMLA 15 minutes application; Intervention D: 1 FTU EMLA Only 30 minutes (controls)

[figure not shown]

Figure 5. Schematic flow of the clinical trial.

GANTT CHART

| Project Activities | Timeline of event | | | | | | | | | | | | | | |
|---------------------------------------|-------------------|---|---|---|---|---|---|---|----|----|----|---|------|---|---|
| | 2021 | | | | | | | | | | | | 2022 | | |
| | 2 | 3 | 4 | 5 | 6 | 7 | 8 | 9 | 10 | 11 | 12 | 1 | 2 | 3 | |
| Proposal preparation | ● | ● | ● | ● | ● | | | | | | | | | | |
| Ethics approval | | | | | ● | ● | | | | | | | | | |
| Microneedle fabrication | | | | | ● | ● | ● | | | | | | | | |
| Purchasing of PainMonitor | | | | | ● | ● | ● | | | | | | | | |
| Patients' recruitment | | | | | | ● | ● | ● | | | | | | | |
| Launching of clinical trial | | | | | | ● | ● | ● | ● | ● | ● | ● | ● | ● | ● |
| Data analysis and interpretation | | | | | | | | ● | ● | ● | ● | ● | ● | ● | ● |
| Manuscript preparation and submission | ● | ● | ● | ● | ● | ● | ● | ● | ● | ● | ● | ● | ● | ● | ● |
| End of research project | | | | | | | | | | | | ● | ● | ● | |

BUDGET

| No. | Description | Unit price (RM) | Quantity | Price (RM) |
|-----|---|-----------------|----------|-----------------|
| 1 | RESEARCH MATERIALS & SUPPLIES | | | |
| 1.1 | Schlenker VAS Pain Scale Rulers 0-100mm with Slider | 40 | pcs | 4 160 00 |
| 1.2 | EMLA Cream 5%, 5G, 1s x 5 | 160 | Box | 12 1920 00 |
| 1.3 | Hansaplast Sensitive Kids Plaster 20's | 6 | box | 7 42 00 |
| | | | | |
| 2 | PROFESSIONAL SERVICE | | | |

APPENDIX III

| LOCAL SKIN REACTIONS | GRADES | | | | |
|----------------------|---------|--|---|--|--|
| | 0 (Nil) | 1 (Mild) | 2 (Moderate) | 3 (Severe) | 4 (Life Threatening) |
| Pain | Nil | Does not interfere with activity | Repeated use of non-narcotic pain reliever for more than 24 hours or interferes with activity | Any use of narcotic pain reliever or prevents daily activity | Emergency room (ER) visit or hospitalization |
| Erythema | Nil | 2.5 cm – 5 cm | 5.1 cm – 10 cm | >10 cm | Necrosis or exfoliative dermatitis |
| Ecchymosis | Nil | 2.5 cm – 5 cm | 5.1 cm – 10 cm | > 10 cm | ER visit or hospitalization |
| Swelling | Nil | 2.5 cm – 5 cm and does not interfere with activity | 5.1 cm – 10 cm or interferes with activity | >10 cm or prevents daily activity | Necrosis |
| Pruritus | Nil | Mild or localized, requires topical intervention | Widespread and intermittent, limiting instrumental activity of daily living (ADL), requires oral intervention | Widespread and constant, limiting self-care ADL, requires systemic corticosteroid or immunosuppressive therapy | - |
| Tenderness | Nil | Mild discomfort to touch | Discomfort with movement | Significant discomfort at rest | ER visit or hospitalization |

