3.9 Clinical protocols

3.9.1 Fabrication of solid maltose microneedle

The MN array patch size is measured 1 cm x 1 cm, containing 36 microneedles with 1 mm needle gap in between. The maltose (Hayashibara, Okayama, Japan) MN dimension is designed to be around 400 μm in height, base width 100 μm , with a 3- μm tip radius. The standard deviation of needle heights within the patch is controlled to be less than 3%. The total patch thickness is therefore 0.8 mm. The MNs are grown on a soft cushion on top of Polyvinyl Alcohol (PVA) material (Kanto Chemical, Tokyo, Japan), with a Polyethylene Terephthalate (PET) patch (Acrysunday, Tokyo, Japan) to support the soft PVA patch as below. The base patch spans 125% larger than the array MN patch, with an estimated patch size of 1.5 cm x 1.5 cm. The overall size of the microneedle device is thus 1.7 cm (width) x 4 cm (length) x 0.5 cm (height). Figure 3 illustrates the schematic representation of microneedle prototypes that will be used in this study.

[figure not shown]

Figure 3. The schematic representation of microneedle prototypes.

Since the MN patch will be manually applied to the skin with a normal thumb force, various studies reported the hole diameter should be around $1/3$ of MN length.^{37,38} Therefore, this research's specification is speculated to achieve the desired penetration depth around 160 μm where the epidermal-dermal junction lies. To ensure a uniform force is applied all over the MN patch, the interventionist will stick a pillar handler of a size of 1 cm x 1cm x 4.9 cm on the bottom surface of MN patch with a double sellotape stuck onto it. The application of MN to the skin thus mimics a stamping action.

The maltose dissolving time is about 15s at a temperature between 25 and 30 °C and a humidity of more than 60%. Hence, in normal condition, the maltose MN is able to dissolve into the skin within 1 minute. For storage, the maltose MN is recommended to be stored at room temperature (upper limit not exceeding 40 °C) and at room humidity of less than 60% to avoid melting. The shelf time can last for more than 8 years, provided that the storage temperature is maintained at 25 °C and a room humidity of less than 10%.

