The investigator identified and drew a grid of 1cm × 1cm at the dorsum hand, which served as an ideal site for cannulation. The administrator of intervention (procedurist) will apply either 1 FTU of EMLA Cream (approximately 0.68 g/cm²) or 0.5 FTU (approximately 0.369 g/cm²) over the preparation area. If the patient is subjected to MN patching at his/her visit, the MN patch will be applied by thumb force and pressed firmly against the hand surface for 5 seconds to patch MN to the skin entirely before applying EMLA cream. Otherwise, an empty (i.e. without MN) PVA-containing PET sham patch will be applied instead. Besides, the height-to-base ratio (4:1) used for MN will also optimally minimise its adverse effects (pain, redness), thus preserving the masking (blinding) of study participants from knowing the types of interventions received. The preparation area will be covered with an adhesive dressing (Tegaderm™; 3M, Maplewood, Minnesota, USA) after EMLA cream application. After the allocated application time (15 or 30 minutes), the attending medical officer will set up the transfusion line with a 22-gauge hypodermic needle inserted into the dorsum hand. Throughout the process, the parents/guardians will be allowed to stay by the patient's side at all times.

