3.10.7 Study Halting Criteria

Participant enrolment and allocation and institution of interventions will be stopped if one of the following occur:

- a) Death related to microneedle or EMLA application
- b) Any participant experiences bronchospasm, laryngospasm or anaphylaxis within 24 hours post microneedle or EMLA application
- c) Any SAE related to microneedle or EMLA application
- d) Any AE of grade 3 and above or any SAE that cannot obviously be implicated on other causes
- e) Any study participant who develops abscess / ulceration / erosion at the site(s) of microneedle or EMLA application

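### The adverse event grading tables leave values without a grade: patch-sized skin reactions under 2.5 cm, and systolic 80 mmHg on the border that triggers reporting and halting

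*Combined protocol and SAP*

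**What the plan says.** Section 3.10.3 of the combined protocol and SAP requires all AEs and SAEs to be recorded and graded under two published toxicity scales, in the form set out in Appendices III and IV.

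Appendix III grades three of the six solicited local reactions by size. The erythema row runs "Erythema | Nil | 2.5 cm – 5 cm | 5.1 cm – 10 cm | >10 cm" and the ecchymosis row starts "Ecchymosis | Nil | 2.5 cm – 5 cm". Swelling has the same lower limit with a functional condition: grade 1 is "2.5 cm – 5 cm and does not interfere with activity". Its grades 2 and 3 can be reached either by size or by interference with activity. Pain, pruritus and tenderness are graded by severity or function, not by size.

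Section 3.9.1 describes the product: "The MN array patch size is measured 1 cm x 1 cm, containing 36 microneedles", on a base "with an estimated patch size of 1.5 cm x 1.5 cm". Section 3.9.2 says the investigator "drew a grid of 1cm × 1cm at the dorsum hand" to mark the site, and it names pain and redness as adverse effects of the microneedle.

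Appendix IV grades fever, tachycardia and hypotension by numeric cut-points. Two rules use the resulting grade. Section 3.10.6 sends events of grade 3 and above to the ethics committee within 5 business days. Criterion d of section 3.10.7 stops enrolment and interventions for "Any AE of grade 3 and above or any SAE that cannot obviously be implicated on other causes".

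**The concern.** A grading rule works only if every observation falls in exactly one grade. Here it does not, in two places.

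The first gap lies where the product acts. A patch little more than a centimetre across can be expected to leave a mark of about its own size, and section 3.9.2 itself expects some redness. A mark of that size is present, so it is not Nil, yet it is too small for grade 1. The assessor must improvise, and different assessors may choose differently. If they tend towards Nil, a table of local reactions by grade will show fewer microneedle reactions than occurred. Tolerability is a large part of what a phase II paediatric study of a skin device should describe.

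The second gap is narrow but lies on a decision border. A child with a systolic pressure of exactly 80 mmHg belongs to no grade, and the two neighbouring grades have different consequences for reporting and halting.

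**Working it through.** **Inputs.** Array 1 x 1 cm, base patch 1.5 x 1.5 cm and whole device 1.7 x 4 cm (section 3.9.1); marked skin area 1 x 1 cm (section 3.9.2); grade limits (Appendices III and IV); rules that use the grade (sections 3.10.6 and 3.10.7).

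**Step 1: the plan's own figure.** Section 3.9.1 says the base is 125% larger than the array. By area, (1.5 × 1.5 − 1 × 1) / (1 × 1) = 1.25, or 125%. The stated 1.5 cm side is reproduced.

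**Step 2: largest reaction confined to the patch.** The longest line across a square is side × √2.
- Array: 1.0 × √2 = 1.41 cm.
- Base patch: 1.5 × √2 = 2.12 cm.

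Both are below 2.5 cm; even the base patch diagonal falls short by 2.5 − 2.12 = 0.38 cm.

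**Step 3: scan of the size scale.** In steps of 0.1 cm, every value from 0.1 to 2.4 cm has no grade, and there is no further gap above that. Reactions of 1.0, 1.5, 1.7 and 2.12 cm are ungraded. A reaction of 4 cm, the length of the whole device, is grade 1.

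**Step 4: swelling.** A swelling under 2.5 cm that interferes with activity meets the alternative condition of grade 2, and one that prevents daily activity meets that of grade 3. Only small swellings that do not interfere are left without a grade. Erythema and ecchymosis have no such functional route.

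**Step 5: scan of Appendix IV**, in steps of 1 bpm, 1 mmHg and 0.1 °C.

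| Row | Grade limits, 0 upwards | Value with no grade | Lies between grades |
|---|---|---|---|
| Tachycardia (bpm) | below 100; 101–115; 116–130; above 130 | 100 | 0 and 1 |
| Systolic pressure (mmHg) | 90 or more; 85–89; 81–84; below 80 | 80 | 2 and 3 |
| Fever (°C) | below 38.0; 38.0–38.4; 38.5–38.9; 39.0 to below 40.0; above 40.0 | 40.0 | 3 and 4 |

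**Step 6: which gaps reach a decision.** Reporting and halting both start at grade 3. At 100 bpm neither neighbouring grade triggers them. At 40.0 °C both neighbouring grades do, so the action is the same. At 80 mmHg one neighbour triggers them and the other does not, so the protocol does not say whether either rule applies.

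**The case against.** The strongest reply is that small reactions are not lost. Section 3.10.4 has the site examined before cannulation and after transfusion, with photographs and a telephone call within 24 hours. It has every local reaction described by maximum intensity, duration, action taken, causal link and course, and section 3.10.6 puts all AEs in the CRF. None of this depends on size. That stands: only the grade is undefined. It does not close the gap, because section 3.10.3 asks for a grade as well and diameter is not among the listed items.

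A reader might infer that a comparison of microneedle with sham would look clean whatever the true reaction rate. The documents do not support that. The reactions are recorded, those extending to 2.5 cm or more would be graded, and neither the objectives in section 2.2 nor the analysis in section 3.14 plans a comparison of graded events. Nor can the extent of under-counting be calculated, because no reaction rate is given.

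A reader might also take any reaction the size of the device to be ungradable. The whole device is 4 cm long, so the statement holds only for the patch footprint. The site also receives EMLA, an adhesive dressing and a 22-gauge needle, so bruising or swelling may spread past that outline.

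Two further points stand. A gap between Nil and grade 1 does not touch reporting or halting, and section 3.10.7 separately halts the study for abscess, ulceration or erosion without any size limit. And the 2.5 cm limit may be deliberate and taken from a cited scale, which cannot be checked from the documents. Even so, the plan grades events as the appendices show them, and an assessor working from those has no entry for a smaller reaction.

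**Conclusion.** The point holds as a defect in the grading tables. Erythema and ecchymosis under 2.5 cm, and non-interfering swelling under 2.5 cm, cannot be graded as section 3.10.3 requires. That range contains every reaction confined to the array or base patch. The gap affects three of six local reactions, swelling only in part. Of the three, section 3.9.2 names only redness as a microneedle effect. The consequence is that a graded summary could under-count patch-sized reactions, not that they go unrecorded.

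In Appendix IV three single values have no grade. Because grade 3 is a halting threshold, a reader might infer that all three matter for stopping; only systolic 80 mmHg does.

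The conclusion assumes that the centimetre limits refer to the largest dimension of the reaction, which Appendix III does not state, and that readings are recorded to 0.1 cm, 0.1 °C, 1 bpm and 1 mmHg. Finer recording would open further small gaps, for example between 5 and 5.1 cm. The primary endpoint is unaffected. The repair is worth making because it is cheap and because a stated safety rule cannot at present be applied to a foreseeable observation.

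**What to change.** - Reconcile Appendices III and IV so that every possible value has exactly one grade, including a reaction that is present but under 2.5 cm and the values 100 bpm, systolic 80 mmHg and 40.0 °C. Where each boundary falls is for the sponsor's clinical team to decide; none is proposed here.
- State in Appendix III which dimension of the reaction the centimetre limits refer to.
- Add a CRF field for the largest diameter of erythema, ecchymosis and swelling, completed at the two inspections already planned in section 3.10.4.
- Add to section 3.14 a descriptive summary of local reactions by treatment, giving presence (yes or no) and diameter alongside the grade, so that the safety description does not depend on the grade limits.

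The cost is two table edits, one CRF field and a short addition to the analysis section. No extra visit or inspection is needed. The downside is that more low-grade events may be reported.

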APPENDIX IV

| SYSTEMIC REACTIONS | GRADES | | | | |
|--------------------------------------|--------------|--|---|--|--|
| | 0 (Nil) | 1 (Mild) | 2 (Moderate) | 3 (Severe) | 4 (Life Threatening) |
| Fever | <38.0 °C | 38.0 – 38.4 °C | 38.5 – 38.9 °C | 39.0 - <40.0 °C | >40.0 °C |
| Tachycardia (bpm) | <100 | 101-115 | 116-130 | >130 | ER visit or hospitalization |
| Hypotension (systolic; mm/Hg) | 90 and above | 85-89 | 81-84 | <80 | ER visit or hospitalization for hypotensive shock |
| Seizure | Nil | Brief partial seizure and no loss of consciousness | Brief generalised seizure | New onset seizures (partial or generalised). Multiple seizures despite medical intervention | Prolonged repetitive seizures, life threatening consequences |
| Irritability | Nil | Mild; easily consolable; No interference with activity | Moderate; limiting instrumental ADL, increased attention indicated; medical intervention is not indicated | Severe abnormal or excessive response; limiting self-care ADL; inconsolable; medical / psychiatric intervention is indicated | ER visit or hospitalization |

| | | | | | |
|-----------------------------|-----|---|---|---|---|
| Tiredness / Lethargy | Nil | Mild symptoms; no interference with daily activity; reduced alertness and awareness | Moderate symptoms; limiting instrumental ADL; no medical intervention is required | Prevents daily activity; requires medical intervention | ER visit or hospitalization |
| Anorexia | Nil | Loss of appetite without alteration in eating habits | Oral intake altered without significant weight loss or malnutrition; oral nutritional supplements indicated | Associated with significant weight loss or malnutrition (e.g., inadequate oral caloric and / or fluid intake) | Life threatening consequences / urgent intervention is required |
| Vomiting | Nil | No interference with daily activity or 1-2 episodes / 24 hours | Some interference with daily activity or >2 episodes / 24 hours | Prevents daily activity, requires outpatient IV hydration | ER visit or hospitalization due to hypotensive shock |

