3.10 Interventional safety assessment

3.10.1 Adverse Events (AEs) / Serious Adverse Events (SAEs): Definitions

For this study, the study investigators define adverse events as “an abnormal sign, symptom, laboratory test, syndromic combination of such abnormalities, untoward or unplanned occurrence (e.g. an accident), or any unexpected deterioration of concurrent illness”.³⁹ For serious adverse events (SAEs), they are defined according to the USA Code of Federal Regulations Title 21, Section 312.32 which is “adverse events result in the following outcomes: 1) death; 2) life-threatening AEs; 3) inpatient hospitalization or prolongation of existing hospitalization; 4) a persistent or significant incapacity or substantial disruption of the ability to conduct normal life functions, or a congenital anomaly / birth defect”.⁴⁰ Other significant medical events are also considered as SAEs if the events compromise the study participants and result in the requirement of medical or surgical intervention to prevent one of the outcomes above. As an example, allergic bronchospasm requiring intensive treatment in an emergency setting to prevent the outcomes above.

3.10.2: The likelihood of AEs / SAEs: Classification of causality

The likelihood of AEs and SAEs are classified based on the modified Naranjo et al. 1981 recommendations as follows:⁴¹

- a) **Unrelated:** The AEs / SAEs are unlikely related to microneedle or EMLA application.
- b) **Possible:** The connection between AEs / SAEs with microneedle or EMLA cannot be excluded with absolute certainty:

- i) There is a temporal relationship between the microneedle / EMLA application with the occurrence of AEs / SAEs.
- ii) However, there is an alternative factor (e.g. characteristic of patient's disease / clinical state) that can possibly or likely explain such a relationship or a significant uncertainty exists over the cause of AEs / SAEs
- c) **Probable:** The connection between AEs / SAEs with microneedle or EMLA has a high degree of certainty
 - i) There is a temporal relationship between the microneedle / EMLA application with the occurrence of AEs / SAEs
 - ii) AEs / SAEs disappear or decreases upon the withdrawal of microneedle or EMLA application but do not reappear upon subsequent microneedle / EMLA application
 - iii) Alternative causes cannot reasonably explain the relationship between microneedle / EMLA application with the occurrence of AEs / SAEs.

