3.10.3 Methods for assessing and recording of AEs / SAEs

The study protocol will be halted at any moment of the study period if the study participants develop any sudden (expected or unexpected) severe complications / adverse events. The withdrawal of a study participant from the trial will be documented on the adverse event page of the CRF and the participant will be further followed up for the study outcomes and included in the analysis as per the original randomization group (intention-to-treat analysis). All AEs / SAEs will be recorded and graded according to the Common Terminology Criteria for Adverse Events (CTCAE) version 5 and US FDA's Toxicity Grading Scale Healthy Adults and Adolescents Volunteers Enrolled in Preventive Vaccine Clinical Trials criteria as shown in Appendix III and IV.^{42,43}

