3.10.5. Systemic Reaction

Among systemic AEs / SAEs associated with study interventions that will be solicited and documented are as follows:

- Fever
- Irritability
- Tiredness
- Anorexia
- Vomiting
- Tachycardia
- Seizure
- Hypotension

Similar safety protocol will be adhered to as in 3.10.4 with adjustments made for systemic reactions.

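### Appendix IV leaves heart rate 100 bpm, systolic pressure 80 mmHg and fever 40.0 °C in no grade; the systolic gap lies on the boundary that triggers reporting and halting review

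*Combined protocol and SAP*

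**What the plan says.** Section 3.10.3 says that all adverse events will be recorded and graded by CTCAE version 5 and a US FDA toxicity scale for volunteers "Enrolled in Preventive Vaccine Clinical Trials criteria as shown in Appendix III and IV". Section 3.10.5 lists fever, tachycardia and hypotension among the solicited systemic reactions.

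Appendix IV gives the numeric limits. For grades 0 to 3 the heart-rate row is "Tachycardia (bpm) | <100 | 101-115 | 116-130 | >130" and the systolic row is "Hypotension (systolic; mm/Hg) | 90 and above | 85-89 | 81-84 | <80". Grade 4 in both rows is defined by an event (an emergency room visit or hospitalization), not by a number. The fever row ends with grades 3 and 4 as "39.0 - <40.0 °C | >40.0 °C".

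Two rules depend on the grade. Section 3.10.6 sends events of grade 3 and above to the ethics committee within 5 business days. Section 3.10.7, rule d, stops enrolment, allocation and interventions for an event of grade 3 and above that cannot obviously be put down to another cause.

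**The concern.** A grading table has to give every possible reading exactly one grade. In each of the three vital-sign rows one boundary value is covered by neither neighbouring cell. This matters most where the two neighbouring grades lead to different actions. At the grade 2/3 boundary they do: grade 2 goes on the case report form only, while grade 3 goes to the ethics committee and may stop the trial. If the value on that boundary has no grade, the step that follows depends on the assessor and not on the protocol.

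**Working it through.** **Inputs.** The cut-offs are those printed in Appendix IV. I assume that heart rate and systolic pressure are recorded in whole units and temperature to 0.1 °C.

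**Method.** Each row was coded as printed. Every value was then tested for membership of no grade or of more than one: heart rate 40 to 220 bpm, systolic pressure 40 to 180 mmHg, temperature 35.0 to 42.9 °C.

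| Row | Cells on either side of the gap | Ungraded value | Values in two grades |
|---|---|---|---|
| Heart rate | grade 0: < 100; grade 1: 101-115 | 100 bpm | none |
| Systolic pressure | grade 2: 81-84; grade 3: < 80 | 80 mmHg | none |
| Fever | grade 3: 39.0 to < 40.0; grade 4: > 40.0 | 40.0 °C | none |

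**Slip or convention?** Other boundaries in the same rows close properly. Fever grade 0 is below 38.0 °C and grade 1 starts at 38.0 °C. Systolic grade 0 is 90 and above and grade 1 stops at 89. The table therefore has no general practice of leaving boundaries open. The cells are fully legible, so this does not look like damage from the PDF conversion.

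**What follows from each gap.**

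- Heart rate 100 lies between grades 0 and 1. Neither grade reaches the reporting or halting threshold. The only question is whether a mild event is written down.
- Fever 40.0 °C lies between grades 3 and 4. Both are at or above the threshold in 3.10.6 and in 3.10.7 rule d, so the event is reported and reviewed under either label.
- Systolic 80 lies between grades 2 and 3. Read as grade 2, it is recorded and no report is due on grade. Read as grade 3, it is reported within 5 business days and falls under rule d unless another cause is obvious.

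**After the fix.** With heart rate grade 0 at ≤ 100, systolic grade 3 at ≤ 80 and fever grade 4 at ≥ 40.0 °C, the sequences are:

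- heart rate: ≤ 100, 101-115, 116-130, > 130;
- systolic pressure: ≥ 90, 85-89, 81-84, ≤ 80;
- upper fever grades: 39.0 to < 40.0, ≥ 40.0.

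At the stated recording precision no value is left out and none falls in two grades.

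**The case against.** The best defence is that little turns on this. A systolic pressure of 80 is not lost: 3.10.6 has every adverse event recorded on the case report form. If the child needed intervention to prevent a serious outcome, the event would be serious under 3.10.1 and reported within 24 hours whatever its grade. The exposed case is one whole-number reading without such intervention. This stands, and it keeps the point small.

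A second defence is that the two source scales named in 3.10.3 may settle the boundaries. They are not among the documents and I cannot check them. However, 3.10.3 points to the appendices for the criteria to be used, so an assessor working from the protocol meets the gap.

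A reader might also infer something stronger: that because Appendix IV uses one absolute cut-off per grade from age 6 to below 18, with no requirement that a value be new or worse than before the patch, pre-existing heart rates or pressures will be counted as reactions and distort the safety results. It is true that no readable rule states such a condition. The documents still do not support the inference, for these reasons:

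- Section 3.10.1 starts from "an abnormal sign, symptom, laboratory test, syndromic combination of such abnormalities, untoward or unplanned occurrence (e.g. an accident"), and attribution comes afterwards. In 3.10.2 the categories possible, probable and definite each require a temporal relationship. The possible category also allows for an alternative factor "that can possibly or likely explain such a relationship", and an unrelated category exists.
- Section 3.10.5 adds "Similar safety protocol will be adhered to as in 3.10.4 with adjustments made for systemic reactions", and 3.10.4 has causal link and evolution documented. Recording first and attributing later is a defensible, cautious choice in a paediatric study.
- The number of children affected cannot be derived and may be zero. Section 3.14 plans no comparison of adverse event rates, and the VAS endpoint is not touched.
- Figure 5 and the case report forms are not in the supplied text, so a pre-patch reading may exist.
- A new-or-worse rule has its own cost. If applied by grade, it would leave uncounted a rise from 101 to 115 bpm, which stays within grade 1. It would also depend on a pre-transfusion reading that can only be assumed to be routine.

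**Conclusion.** The concern holds for the three boundary values and no further. Appendix IV as printed leaves heart rate 100 bpm, systolic pressure 80 mmHg and fever 40.0 °C without a grade. One of the three, systolic 80, sits on a decision threshold, where the plan permits two different actions for the same reading. The other two are labelling slips with no effect on reporting or halting.

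The size is one ungraded value per row, given readings in whole bpm, whole mmHg and tenths of a degree. The frequency of a systolic reading of exactly 80 is unknown and may be nil. The primary endpoint, the sample size and the comparison between interventions are unaffected. The correction is worth making because it costs almost nothing, but the trial does not depend on it.

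**What to change.** Change three cells in Appendix IV:

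1. Heart rate, grade 0: 100 bpm or below.
2. Systolic pressure, grade 3: 80 mmHg or below.
3. Fever, grade 4: 40.0 °C or above.

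The systolic gap could instead be closed by widening grade 2 to 80-84, but that would put the one value that matters on the non-reporting side. The cautious side is preferable in children.

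The cost is wording only: no added measurement, no new form field and no change to the analysis. The downside is that a systolic reading of exactly 80 becomes reportable to the ethics committee within 5 business days and subject to halting rule d unless another cause is obvious.
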